9.5.2. Vital signs

Table 67. Change in heart rate from baseline at each visit

Items	Indicator	Experimental group	Control group	Total
Baseline	N (Missing) Mean (SD) Median Q1, Q3 Min, Max 95%CI			
Between-group comparison in baseline	Statistics P-value			
Visit 2/Day 7±3	N (Missing) Mean (SD) Median Q1, Q3 Min, Max 95%CI			
Between-group comparison in Visit 2/Day 7±3	Statistics P-value			
Change in Visit 2/Day 7±3 from baseline	N (Missing) Mean (SD) Median Q1, Q3 Min, Max 95%CI			
Pre- and post-treatment comparison of intra-group	Statistical method Statistics P-value			
Comparison of changes between groups pre- and post-treatment	Statistics P-value			
Visit 4/Day 56±7	N (Missing) Mean (SD)			

Items	Indicator	Experimental group	Control group	Total
Between-group comparison in Visit 4/Day 56±7	Median Q1, Q3 Min, Max 95%CI Statistics P-value			
Change in Visit 4/Day 56±7 from baseline	N (Missing) Mean (SD) Median Q1, Q3 Min, Max 95%CI			
Pre- and post-treatment comparison of intra-group	Statistical method Statistics P-value			
Comparison of changes between groups pre- and post-treatment	Statistics P-value			
Visit 5/Day 112±7	N (Missing) Mean (SD) Median Q1, Q3 Min, Max 95%CI			
Between-group comparison in Visit 5/Day 112±7	Statistics P-value			
Change in Visit 5/Day 112±7 from baseline	N (Missing) Mean (SD) Median Q1, Q3 Min, Max 95%CI			
Pre- and post-treatment comparison of intra-group	Statistical method			

Items	Indicator	Experimental group	Control group	Total
Comparison of changes between groups pre- and post-treatment	Statistics P-value			
Visit 6/Day 168±7	Statistics P-value N (Missing) Mean (SD) Median Q1, Q3 Min, Max 95%CI			
Between-group comparison in Visit 6/Day 168±7	Statistics P-value			
Change in Visit 6/Day 168±7 from baseline	N (Missing) Mean (SD) Median Q1, Q3 Min, Max 95%CI			
Pre- and post-treatment comparison of intra-group	Statistical method Statistics P-value			
Comparison of changes between groups pre- and post-treatment	Statistics P-value			
Visit 7/Day 224±7	N (Missing) Mean (SD) Median Q1, Q3 Min, Max 95%CI			
Between-group comparison in Visit 7/Day 224±7	Statistics P-value			
Change in Visit 7/Day 224±7 from baseline	N (Missing)			

Items	Indicator	Experimental group	Control group	Total
Pre- and post-treatment comparison of intra-group	Mean (SD) Median Q1, Q3 Min, Max 95%CI Statistical method Statistics P-value			
Comparison of changes between groups pre- and post-treatment	Statistics P-value			
Visit 8/Day 280±7	N (Missing) Mean (SD) Median Q1, Q3 Min, Max 95%CI			
Between-group comparison in Visit 8/Day 280±7	Statistics P-value			
Change in Visit 8/Day 280±7 from baseline	N (Missing) Mean (SD) Median Q1, Q3 Min, Max 95%CI			
Pre- and post-treatment comparison of intra-group	Statistical method Statistics P-value			
Comparison of changes between groups pre- and post-treatment	Statistics P-value			
Visit 9/Day 364±7	N (Missing) Mean (SD) Median			

Items	Indicator	Experimental group	Control group	Total
Between-group comparison in Visit 9/Day	Q1, Q3 Min, Max 95%CI Statistics P-value			
Change in Visit 9/Day	364±7			
Change in Visit 9/Day	364±7 from baseline	N (Missing) Mean (SD) Median Q1, Q3 Min, Max 95%CI		
Pre- and post-treatment comparison of intra-group	Statistical method Statistics P-value			
Comparison of changes between groups pre- and post-treatment	Statistics P-value			

Table 68. Change in respiratory rate from baseline at each visit

Ibid.

9.5.3. Blood routine examination

Table 69. Summary of blood routine examination-Leukocyte count (WBC)

Items	Indicator	Experimental group	Control group	Total
Visit 1/Day 0	Within the normal range n (%) Below the normal range n (%) Higher than the normal range n (%) Total (Missing) Statistics P-value			

Visit 9/Day 364±7	Within the normal range n (%)
	Below the normal range n (%)
	Higher than the normal range n (%)
	Total (Missing)
	Statistics
	P-value

Table 70. Summary of blood routine examination-Lymphocyte percentage (LY)

Items	Indicator	Experimental group	Control group	Total
Visit 1/Day 0	Within the normal range n (%)			
	Below the normal range n (%)			
	Higher than the normal range n (%)			
	Total (Missing)			
	Statistics			
	P-value			
Visit 9/Day 364±7	Within the normal range n (%)			
	Below the normal range n (%)			
	Higher than the normal range n (%)			
	Total (Missing)			
	Statistics			
	P-value			

Table 71. Shift-table of blood routine examination results before and after treatment-Leukocyte count (WBC)

Group	Before treatment	Day 364±7 after treatment					Not tested	Missing	Total
		Normal	Abnormal but not clinically significant	Abnormal and clinically significant					
Experimental group	Normal								
	Abnormal but not clinically significant								
	Abnormal and clinically significant								
	Not tested								

	Missing
	Total
Control group	Normal
	Abnormal but not clinically significant
	Abnormal and clinically significant
	Not tested
	Missing
	Total

Table 72. Shift-table of blood routine examination results before and after treatment-Erythrocyte count (RBC)

Ibid. Same below.

Table 73. Shift-table of blood routine examination results before and after treatment-Haemoglobin (Hb)

Table 74. Shift-table of blood routine examination results before and after treatment-Platelet count (PLT)

Table 75. Shift-table of blood routine examination results before and after treatment-Lymphocyte percentage (LY)

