8.3 Records of adverse events

The information of AEs to be collected in this research includes the following aspects:

- Endpoint event
- Adverse events related to the test drugs (according to the judgment of the investigators)
- Serious adverse event

Cycle of adverse event collection

The collection of AEs and adverse drug reactions (DAEs) of concern will be carried out throughout this research, from randomization to site close-out visit (SCV, included).

SAE records will be carried out throughout this research, from the time of signing the Informed Consent Form to SCV (included).

Follow-up of unresolved adverse events

If any AE, DAE and SAE of concern remain unresolved at the patient's last study visit, the investigators shall follow up these events in accordance with the medical instructions as required for medical needs in this research, but it is not necessary to record further in the electronic case report form (eCRF). If deemed necessary, the Sponsor reserves the right to obtain the additional information on unresolved AE/SAE of concern.

Variables

For each non-serious AE and DAE of concern, the following variables will be collected:

- AE (verbatim record);
- AE start and end dates;
- Maximum intensity;

- Whether the AE is serious;
- The investigators' assessment of the causal relationship with the test drug (yes or no);
- Measures and outcomes taken for the test drug

In addition, the following variables will be collected for SAE:

- Date when AE meets SAE criteria;
- Date when the investigators find SAE;
- Reasons for classifying AE as SAE;
- Date of admission;
- Date of discharge;
- Possible causes of death
- Date of death;
- Autopsy performed (if any);
- Autopsy results
- AE description
- Assessment of causality with this research procedure;
- Assessment of causality with the other drugs

It is important to distinguish serious AE from severe AE. Severity is the index of intensity evaluation, while seriousness is defined according to the criteria in Section 8.2. AE with severe intensity is not necessarily serious. For example, nausea for several hours may be considered as severe nausea, but not SAE. On the other hand, a stroke that results in only a limited degree of disability may be considered as a mild stroke, but should be considered as SAE.

The definition of intensity classification is as follows:

1. Mild (signs or symptoms are felt but easily tolerated)

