2. Moderate (the degree of discomfort is enough to interfere with normal activities)
3. Severe (resulting in disability and inability to perform normal activities)

Collection of causalities

The investigators will assess the causalities between the test drugs and each case of AE, and answer the following questions with "Absolutely related, Probably related, Possibly related, Possibly unrelated, and Unrelated".

"Do you think there is a reasonable possibility that the event is caused by the test drug?"

For SAE, the causalities between the event and other drugs and research procedures also need to be evaluated. Note: for SAE related to any research procedure, causality should be "possibly related".

Adverse events based on signs and symptoms

All concerned AEs (see sections 8.1.1 and 8.1.2), including those spontaneously reported by the patients, those reported in response to the open-ended question by the investigators, "Have you

had any health problems since the last visit/inquiry?", or those found through observation will be all collected and recorded in eCRF. In the collection of AE information, the list of signs and symptoms shall be preferred as the record of diagnosis (if possible). However, if the diagnosis is known and there are other signs or symptoms not usually present in the diagnosis, the diagnosis and each other sign or symptom shall be recorded separately.

Adverse events based on examination and inspection

During this research, the laboratory safety assessment will not be carried out routinely (except at baseline), but can be carried out at the discretion of the investigators. When an AE, DAE, SAE or potential endpoint of concern is involved, different assessments may be required, including local laboratory assessment, and appropriate collection is needed before entry into eCRF.

The examination results of vital signs mandated by the Protocol shall be summarized in the clinical study report (CSR). Therefore, when the laboratory test values and protocol-mandated vital signs evaluation by the investigators show that the results are worse than the baseline level and meet the AE criteria or when they act as are the reasons for discontinuing the test drug treatment, such situations will be reported as AE.

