4.3. Research plan

4.4. Clinical trial flow chart

Clinical trial flow chart

Items	Screening and enrollment period		Treatment and follow-up period							
	Screen (V0)	Visit 1 (V1)	Visit 2 (V2)	Visit 3 (V3)	Visit 4 (V4)	Visit 5 (V5)	Visit 6 (V6)	Visit 7 (V7)	Visit 8 (V8)	Visit 9 (V9)
Follow-up week	Day -30 - 0	Included	Day 7	Day 28	Day 56	Day 112	Day 168	Day 224	Day 280	Day 364
Sign the informed consent gorm	✓									
Inclusion/exclusion criteria		✓								

Stop the original immunosuppressants after 2 weeks	\$	\$								
Randomized		√								
General data	√									
Medical history (course of disease, frequency of relapses in 1 year and 6 months before enrollment, steroid dosage)	√									
Vital signs	√	√	√	√	√	√	√	√	√	√
Height and weight	√	√	√	√	√	√	√	√	√	√
Physical examination	√	◎	√	√	√	√	√	√	√	√
Blood routine examination	√	◎	√	√	√	√	√	√	√	√
Urine routine examination	√	◎	√	√	√	√	√	√	√	√

Fasting blood glucose	√		√	√	√	√	√	√	√	√	√
Serum liver function	√	◎	√	√	√	√	√	√	√	√	√
Blood lipid	√	◎	√	√	√	√	√	√	√	√	√
Serum renal function	√	◎	√	√	√	√	√	√	√	√	√
Blood EBV-DNA, and CMV antibody	√										√
24hr urinary protein (>3 years old)	√	◎	√	√	√	√	√	√	√	√	√
Urinary protein / creatinine	√	◎	√	√	√	√	√	√	√	√	√
eGFR	√	◎	√	√	√	√	√	√	√	√	√
Tacrolimus concentration in plasma			√	√	√	√	√	√			√
Mycophenolic acid concentration in plasma			√					√			

Chest X-ray	√									√
ECG	√									√
Markers of hepatitis B and hepatitis C virus	√									
Examination of Mycobacterium tuberculosis and fungi	√									
Biological samples of blood and urine	√						√			√
Drug distribution and measurement		√	√	√	√	√	√	√	√	√
Guidance on the administration of test drug		√	√	√	√	√	√	√	√	√
Clinical efficacy (relapse or no)			√	√	√	√	√	√	√	√

Concomitant medication	√	√	√	√	√	√	√	√	√	√
Adverse event			√	√	√	√	√	√	√	√
Record case report form	√	√	√	√	√	√	√	√	√	√

Remarks:

1. Liver function: ALT, TBIL, ALB; Renal function: creatinine, blood urea nitrogen, uric acid, Cystatin C;
2. Blood lipids: Triglycerides, cholesterol; Urinary protein / creatinine: morning urine; Markers of hepatitis B and hepatitis C virus: HBsAg, HBeAg, HBcAb, HCV;
3. Mycobacterium tuberculosis examination: T-sport; Fungal examination: fungal G test or other; Estimated glomerular filtration rate: eGFR = $K \times \text{height (cm)} / \text{serum creatinine (mg/dL)}$ (see Appendix);
4. Visit time window: ± 3 days for visit 2, and ± 7 days for other visits;

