4.5.4. Withdrawal criteria

Patients are free to withdraw from the trial at any time without any reason.

Patients must withdraw from this research in the following conditions:

- (1) Withdrawal of the Informed Consent Form.
- (2) Violation of the inclusion criteria or compliance with the exclusion criteria.
- (3) No administration of the test drug according to the Protocol for 14 consecutive days due to various reasons.
- (4) For two consecutive times, the measured value of SCr with an interval of at least 4 weeks has increased more than twice the baseline, and eGFR < 60mL/min.1.73m².
- (5) The target concentration of tacrolimus or mycophenolate mofetil can not be reached after dose adjustment for one month.
- (6) ALT or total bilirubin levels reach more than 2 times of the upper limit after medication, with a continuous increase for 2 weeks; if ALT or total bilirubin levels still rise to more than 2 times of the

upper limit after 2 weeks of liver protection drug treatment, stop the test drug. In case of no recovery after 2 weeks of drug withdrawal, the patient shall withdraw from the test.

(7) Occurrence of unknown adverse events of unacceptable nature, severity and/or duration, or occurrence of known unacceptable adverse events or the occurrence frequency exceeding expectations.

(8) The clinical events or safety-affecting events result in withdrawal from the clinical trial, and the investigators believe that such subjects shall withdraw from the trial.

(9) If pregnancy occurs during treatment, withdraw from the trial.

(10) Unauthorized use of drugs prohibited by this research.

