7.1. Analysis data set

Full analysis set (FAS): It refers to the set of eligible cases and drop-off cases. The cases are required to have evaluation data after at least one treatment, but excluding the eliminated cases. Per-protocol set (PPS): It refers to the set of cases that meet the inclusion criteria, do not meet the exclusion criteria and complete the treatment plan, that is, the analysis of cases that meet the trial protocol, have good compliance and complete the specified content in CRF (PP analysis).

Safety set (SS): It refers to the actual data with safety index records after receipt of at least one treatment. The missed safety values shall not be carried forward. It includes some eliminated cases that can be evaluated, such as those whose age exceeds the inclusion criteria, but excludes those whose safety judgment cannot be made due to the use of banned drugs. For the incidence of adverse reactions, the number of cases in the safety set is used as the denominator.

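### The safety-set shift tables for repeated laboratory tests (31 of 34) read only Day 364, so no planned laboratory table counts by arm the children abnormal at any visit; the safety set also omits some treated children

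*SAP*

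**What the plan says.** **Schedule.** The flow chart (SAP 4.4; protocol 1.3) ticks blood and urine routine, fasting glucose, lipids, renal function, urine protein tests, eGFR and "Serum liver function" at each of Visits 2 to 9. Remark 1 lists ALT, total bilirubin and albumin as the liver tests.

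**Shift tables.** Table 71 (SAP 9.5.3) crosses the pre-treatment category with the category at "Day 364±7 after treatment". The categories are normal, abnormal without clinical significance, abnormal with clinical significance, not tested, and missing. A note after Table 72 carries this shell forward. Tables 69 and 70 (leukocytes and lymphocyte percentage, against the normal range) show Visit 1 and Visit 9 only.

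**Adverse event route.** SAP 8.1.6 counts clinically significant laboratory changes as adverse events. Protocol 8.3 adds, for laboratory values, that "when they act as are the reasons for discontinuing the test drug treatment, such situations will be reported as AE". SAP 8.1.5 tests withdrawal or drug change for adverse reactions between arms. The same protocol section says that "the laboratory safety assessment will not be carried out routinely (except at baseline", and its collection list includes "Adverse events related to the test drugs (according to the judgment of the investigators".

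**Safety set.** SAP 7.1 admits some eliminated cases that can be evaluated and "excludes those whose safety judgment cannot be made due to the use of banned drugs". SAP 4.5.4 makes "Unauthorized use of drugs prohibited by this research" a mandatory reason for withdrawal.

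**The concern.** Safety is half of the trial's objective, and the plan itself expects laboratory toxicity to come and go. Protocol 8.1.1 describes the listed tacrolimus reactions as reversible or lessened by dose reduction. SAP 5.2.3 and 5.2.4 tie dose changes to creatinine with eGFR and to blood counts. SAP 5.2.1 sets drug-concentration targets for Visits 2–6 that differ from those for Visits 7–9. Liver and renal criteria can end participation: SAP 4.5.4 begins the renal one "For two consecutive times, the measured value of SCr with an interval of at least 4 weeks has increased more than twice the baseline". A table that looks only at Day 364 is poorly placed to show toxicity that has been acted on, or that ended in withdrawal.

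The number of affected children in each arm would then rest mainly on what open-label investigators report as adverse events.

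The safety-set rule is a separate matter. It removes treated children after randomisation, on a judgement for which the SAP names no criterion, decision-maker or timing.

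**Working it through.** **1. The plan's own figure.** Sample size (SAP 4.2.2): 229 / (1 − 0.15) = 269.4, rounded up to 270, or 135 per arm. This reproduces. It is used here only to scale steps 4 and 5.

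**2. Which tables are affected.**
- Blood routine, 71–75: 5
- Urine routine, 76–81: 6
- Serum biochemistry, 82–98: 17
- EBV-DNA, IgM and IgG, 99–101: 3
- Urine protein tests, 102–103: 2
- eGFR, 104: 1

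The total is 34. Tables 99–101 are set aside because EBV-DNA and CMV antibody are scheduled only at screening and Visit 9, so Day 364 is their only planned later value. That leaves 34 − 3 = 31.

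For these test groups the flow chart gives eight post-baseline visits: Days 7, 28, 56, 112, 168, 224, 280 and 364. The shell reads one. Seven of the 31 analytes (GT, AST, LDH, direct bilirubin, ALP, total protein, globulin) are not named in Remark 1. For them the evidence of repeated values is Tables 41, 43, 44 and 46–49, which are titled as change from baseline at each visit.

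**3. Whether another output supplies the count.**

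| Output | Set | Gives | Lacks |
|---|---|---|---|
| Tables 23–27 and 35–58 (5 + 24 = 29) | FAS/PPS | Means, medians, ranges and P-values by visit and arm | Counts of affected children; safety set; Visit 3 (the Table 23 shell goes from Visit 2 to Visit 4) |
| Listings 121–125 | Safety set | Normal-to-abnormal results with group and visit | Any count |
| Tables 62–66 | Safety set | Adverse events by arm, at any time | Abnormalities not reported as events |

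No row gives a laboratory-based, by-arm, any-visit count on the safety set.

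**4. Size of the under-count.** The documents give no abnormality rates, so this is illustration only. Assume first onset equally likely at each of the 8 visits, a chance q that an abnormality is still present at the next visit, no recurrence and no withdrawal. The share of affected children visible at Day 364 is (1/8) × (1 + q + … + q⁷):
- q = 0: 12.5%
- q = 0.5: 24.9%
- q = 0.8: 52.0%
- q = 1: 100%

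Withdrawal would lower these shares. If the planned 15% loss all meant no Day 364 test, 0.15 × 135 = about 20 children per arm would have no value there.

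**5. Safety set.** Take k children with an event out of 135, and remove one child.
- Child with an event: k/135 − (k − 1)/134 = (135 − k)/18,090. The rate falls by 0.74 points at k = 1, 0.67 at k = 14, 0.37 at k = 68 and 0.15 at k = 108.
- Child without an event: k/134 − k/135 = k/18,090. The rate rises by 0.01, 0.08, 0.38 and 0.60 points at the same k.

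The largest possible shift either way is 134/18,090 = 0.74 points. The documents give no expected number of such children.

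**6. What the scheduled data can determine.** After Visit 2 the gaps between visits are 21, 28, 56, 56, 56, 56 and 84 days. The two-week condition in the ALT/bilirubin withdrawal criterion therefore cannot be assessed from scheduled visits alone.

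**The case against.** The best reply is that little is truly hidden. A laboratory value that stops treatment must be reported as an adverse event, Table 62 counts drop-outs due to adverse events by arm, and drug changes for adverse reactions are compared. The listings already name each newly abnormal child with arm and visit, so a count could be made from a planned output. The by-visit tables show ranges. On this view only a summary format is missing.

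Much of that stands. A reader might infer that laboratory toxicity before Day 364 goes unanalysed; the documents do not support this. But a possible count is not a planned one. The by-visit tables use a set that excludes eliminated cases. Apart from discontinuations, the adverse event route depends largely on investigator judgement without blinding.

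A second reply also stands: the shift categories are themselves clinical-significance judgements. A worst-value table in the same shell would inherit that judgement and largely repeat the adverse event tables, so it would not be an independent check. A normal-range version avoids most of this.

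On the safety set, the SAP does give a ground for exclusion, Tables 2 and 3 count the set by arm, and Tables 109 and 110 flag membership. However, those listings have a reason column for the per-protocol set only.

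**Conclusion.** The point holds as a cheap improvement. Thirty-one safety-set shift tables, with Tables 69 and 70, read one visit for tests that are repeated through the year, and no planned laboratory table counts children ever abnormal by arm on that set. The safety set also has a post-randomisation exclusion without a decision rule.

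Three stronger readings are not supported:
- That all 34 laboratory shift tables lose seven of eight visits. Three cover tests with no planned interim value, and for seven analytes the repetition rests on the by-visit table titles, not on Remark 1.
- That the under-count is known to be large. The 12.5% to 100% range comes from an assumption outside the documents, and its upper end is no loss at all.
- That the safety-set rule materially biases the comparison. The effect is at most about 0.74 points per child at 135 per arm, in either direction, for an unknown number of children.

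The primary relapse result is not affected.

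**What to change.** 1. On the safety set, for laboratory safety parameters measured at repeated visits, add the number and percentage per arm with a value outside the normal range at any post-baseline visit, including unscheduled and withdrawal visits. Give the risk difference and 95% CI. Add a baseline-to-worst shift table using the normal-range categories of Tables 69 and 70, not only the clinical-significance judgement. Keep the Day 364 tables as supplementary.
2. Where the plan's own laboratory thresholds are tabulated, count those the recorded data can determine. Report ALT or bilirubin above twice the upper limit at any visit, and state that the two-week condition cannot be assessed from scheduled visits alone.
3. Define the safety set as every randomised child who took at least one dose. Flag banned-drug use instead of excluding for it.
4. Minor: add Visit 3/Day 28 to the Table 23 and Table 67 shells. Align Table 62 Note 1, which lists all five causality categories, with the three related categories in SAP 8 and 8.1.6. Reconcile the statement in protocol 8.3 that laboratory safety assessment is not routine after baseline with the flow chart.

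The cost is SAP wording, extra programming and longer output. No new visits or tests are needed.
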